6.2.2. ANALYSIS METHODS

Rate of 24-week TI, CR, PR, and hematologic improvement (HI), and other binary endpoints, will be summarized with percentage along with its 95% 2-sided exact Clopper-Pearson confidence interval.

The time to 8-week RBC TI and time to 24-week RBC TI will be summarized descriptively.

The Kaplan-Meier method will be used to estimate the distribution of duration of RBC TI for 8-week and 24-week TI responders, respectively. The distribution of OS and time to progression to AML will be summarized using similar Kaplan-Meier methods.

Amount and relative change in RBC transfusions will be summarized descriptively by time point.

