6. DOSAGE AND ADMINISTRATION

Talacotuzumab and daratumumab are the investigational medicinal products in this study and will be provided by the sponsor.

Subjects may receive treatment until disease progression, lack of response, unacceptable toxicity, withdrawal of consent, or study end. Continuation of treatment for subjects who are not deriving benefit, ie, after 6 months of treatment a subject has not achieved HI-E or RBC TI for ≥ 8 weeks, should be discussed with the sponsor.

Supportive Care

All subjects will receive supportive care (including transfusions if Hb ≤ 11 g/dL or myeloid growth factors) as needed per investigator discretion and according to local standard practices. Should an exceptional situation arise where it is deemed clinically necessary to give a transfusion for an Hb > 11 g/dL, the sponsor should be notified.

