9.2.1. Transfusions

Data to be collected at each visit include the number of units and type of blood products transfused and the pre-transfusion hemoglobin and platelet count. Transfusion data will be collected during the treatment and posttreatment periods as specified in the Time and Event Schedules. Transfusion is monitored at each visit for infusion (every 4-week cycle), at each disease evaluation visit, and at all unscheduled visits during treatment. During the posttreatment phase, transfusion data will be collected every 4 to 6 weeks. Specific operational monitoring will be implemented to seek transfusion information from other documented sources. Specific and continuous medical review will be implemented to identify any sudden but unsustained increase

of Hb values and to query whether transfusion has occurred. Red blood cell transfusions may be administered based on hemoglobin level (sponsor should be notified for Hb >11 g/dL), investigator's assessment of the subject's clinical signs and symptoms, and local clinical practice.

As the volume of 1 unit of RBC transfusion may vary regionally, 1 unit is defined as the amount that is intended to raise Hb by approximately 1 g/dL in an adult patient (ie, 1 standard pRBC unit or equivalent). The total number of RBC units required over consecutive 8-week time periods will be calculated to identify subjects who achieve RBC TI or transfusion reduction.

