10.2. Discontinuation of Study Treatment/Withdrawal from the Study

If a subject's study drug must be discontinued, this will not result in automatic withdrawal of the subject from the study.

Discontinuation of Study Treatment

A subject's study treatment must be discontinued if:

- The investigator believes that for safety reasons (eg, adverse event) it is in the best interest of the subject to discontinue study treatment
- The subject becomes pregnant
- The subject experiences disease progression or relapse
- The subject refuses further treatment
- A serious protocol violation has occurred, as determined by the principal investigator or the sponsor

End-of-treatment and posttreatment follow-up assessments should be obtained. The reason(s) a subject discontinues treatment will be recorded on the eCRF.

Withdrawal From the Study

A subject will be withdrawn from the study for any of the following reasons:

- Lost to follow-up
- Withdrawal of consent
- The sponsor discontinues the study

If a subject is lost to follow-up, every reasonable effort must be made by the study-site personnel to contact the subject and determine the reason for discontinuation/withdrawal. The measures taken to follow-up must be documented.

When a subject withdraws before completing the study, the reason for withdrawal is to be documented in the eCRF and in the source document. Study drug assigned to the withdrawn subject may not be assigned to another subject. Subjects who withdraw will not be replaced. If a subject withdraws from the study before the end of the Treatment Phase, end-of-treatment and posttreatment follow-up assessments should be obtained, unless the subject withdraws consent.

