Time to progression to AML is defined as the interval from Study Day 1 to the date of AML progression (bone marrow or peripheral blood blasts $\geq 20\%$). Subjects who have not progressed to AML at the cutoff date for the analysis or who withdraw from the study will be censored at the date of the last disease evaluation.

Amount and Relative Change in RBC Transfusions

Amount of RBC transfusions is defined as the total number of RBC transfusion units in a given post-baseline 8-week (any consecutive 56 days period) interval during study. The starting date of a post-baseline 8-week interval must be between Study Day 1 and End of treatment Phase ending date (date of last dose of study medication + 30 days). Relative change in RBC transfusions is defined as:

$$\text{Relative change in RBC Transfusion} = \frac{\text{amount of RBC transfusions} - \text{prior RBC transfusion burden}}{\text{prior RBC transfusion burden}} * 100 \%$$

Note that prior RBC transfusion burden is the maximum number of RBC units transfused over an 8-week period during the 16 weeks prior to Study Entry.

The best RBC transfusion reduction is defined as the “best” or the “minimum” number of RBC transfusions in any post-baseline 8-week interval. The time to the best transfusion reduction in an 8-week interval (in weeks), the minimum number of RBC transfusions received during this interval, and the relative change from baseline will be summarized.

Rate and Duration of Myeloid Growth Factor Usage

Rate of myeloid growth factor usage is defined as the proportion of subjects receiving any myeloid growth factors starting from Study Day 1; duration of myeloid growth factor administered starting from Study Day 1.

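### The by-time-point RBC transfusion summary loses subjects soon after they stop drug, so its later rows lean towards responders and overstate the reduction in the ITT population

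*SAP*

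**What the plan says.** SAP 6.2.1 defines the amount of RBC transfusions as the "total number of RBC transfusion units in a given post-baseline 8-week (any consecutive 56 days period) interval during study", and relative change as the percentage difference from the prior burden (the largest 8-week count in the 16 weeks before entry). It then limits the intervals: "The starting date of a post-baseline 8-week interval must be between Study Day 1 and End of treatment Phase ending date", where that ending date is last dose + 30 days. SAP 6.2.2 adds one sentence on analysis: "Amount and relative change in RBC transfusions will be summarized descriptively by time point". It does not define the time points, the denominator at each, or the handling of subjects off drug. The missing-data rule in SAP 6.1.2 covers TI periods only. SAP 4.3 assigns efficacy analyses to the ITT set.

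On stopping, Protocol 6 says: "Subjects may receive treatment until disease progression, lack of response, unacceptable toxicity, withdrawal of consent, or study end". It also asks that continuation be discussed with the sponsor when "after 6 months of treatment a subject has not achieved HI-E or RBC TI" for at least 8 weeks. Protocol 10.2 lists among the reasons for which treatment must be discontinued: "The subject experiences disease progression or relapse".

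On data after stopping, Protocol 9.2.1 says: "During the posttreatment phase, transfusion data will be collected every 4 to 6 weeks". The Time and Events Schedule qualifies this as where feasible.

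**The concern.** A row-by-row mean can be read over time only if the same subjects are in each row, or if those who leave do so for reasons unrelated to the outcome. Here the interval limit removes subjects once they are off drug, and several reasons for being off drug are themselves transfusion outcomes. Those who never responded and those who lost response leave the table, and those still benefiting stay. The mean over those who stay is then better than the mean over the ITT population, although the trial plans to go on collecting transfusions from those who left.

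Rate and amount of supportive care, including transfusions, is a stated secondary objective. Protocol 11.3 and SAP 3.4 say that other endpoints, secondary ones included, carry more weight when 6 or 7 subjects reach TI. SAP 3.6 leaves one analysed arm, so no comparator would show the bias.

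**Working it through.** **The plan's own figure.** The documents give no figure for this summary. The decision rule that gives it weight does reproduce: with 8 TIs in 30 the posterior is Beta(8.5, 22.5), the 80% interval is 17.6% to 37.9%, and the probability of a rate above 15% is 0.955. Six or seven TIs are inconclusive, as stated.

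**Which row is affected first.** Six months is 6 × 30.4375 = 182.6 days (SAP 4.2), about Week 26. For a last dose then, the latest admissible start is 182.6 + 30 = about day 213. Successive 8-week intervals start 0, 56, 112, 168 and 224 days after Study Day 1. The fifth, starting at Week 32, is the first to lose the subject. The limit is on the start, so transfusions up to about 30 + 56 = 86 days after the last dose can still count.

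**Closed form.** Let f be the responder share, s the share of non-responders stopping at about 6 months, and r the responders' mean change, with non-responders at 0%.

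- Mean over all subjects: f × r.
- Mean under the SAP limit: f × r / [f + (1 − f)(1 − s)].

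The second is larger in size whenever s > 0. Take f from the plan's 30% target and 15% minimum acceptable value. Assume that responders fade from -100% in the early intervals to -60% in the fifth.

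| f | Early, all | Fifth, all | Fifth, SAP limit, s = 25 / 50 / 75 / 100% |
|---|---|---|---|
| 30% | -30% | -18% | -21.8 / -27.7 / -37.9 / -60.0% |
| 15% | -15% | -9% | -11.4 / -15.7 / -24.8 / -60.0% |

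Example: f = 30%, s = 50% gives 0.30 × (-60) / (0.30 + 0.70 × 0.50) = -18 / 0.65 = -27.7%.

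The fifth row looks deeper than the early rows only if s > (1 − late r / early r) / (1 − f). That is 0.40 / 0.70 = 57% for f = 30% and 0.40 / 0.85 = 47% for f = 15%. Responders are the majority of those left only if s > 1 − f / (1 − f), which is 57% and 82%.

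**Simulation with gradual onset and loss of response.** N = 30. Assumptions not in the documents:

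- TI onset is uniform over Weeks 0 to 12.
- Responders are transfusion-free during TI and stop drug 4 weeks after relapse.
- Non-responders are unchanged from prior burden.
- TI lasts 8 weeks plus an exponential time with median 37 weeks, so the median total is 45 weeks. The 37 is the midpoint of the 33 to 41 weeks quoted for lenalidomide in Protocol 1.

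Mean change in the interval starting at Week 32:

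| Non-responders stopping early / of the rest, at 6 months | TI rate 30% | TI rate 15% |
|---|---|---|
| All subjects, on or off drug | -20% | -10% |
| SAP limit, 0% / 25% | -26% | -13% |
| SAP limit, 10% / 25% | about -28% | not reported |
| SAP limit, 10% / 50% | -35% | -20% |
| SAP limit, 20% / 80% | -55% | -38% |
| SAP limit, 20% / 100% | -80% | -79% |

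Row by row at a TI rate of 30%:

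- With 10% / 25% stopping, the intervals starting at Weeks 16, 24, 32 and 40 show about -28, -25, -28 and -25%. This is flat, while the all-subject mean falls to -20% and -17% in the last two.
- With 10% / 50%, the table moves from -25% (Week 24) to -35% (Week 32), while the all-subject mean moves from -23% to -20%.
- With 20% / 80%, it moves from -26.3% to -55.1% and then -52.6%, on about 11 and 10 subjects.

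The fade here is slower (all-subject mean from -27% to -20%, ratio 0.74), so the closed-form threshold falls to 0.26 / 0.70 = 37%. Setting the median total TI duration to 37 weeks moves the 20% / 80% result from about -55% to -51%.

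**The case against.** The limit may be a deliberate on-treatment convention, since the same one applies to 8-week and 24-week TI. It acts differently there. A subject with no qualifying TI period stays in the denominator as a non-responder (SAP 6.1.2), whereas here the subject leaves the row.

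A reader might infer that non-responders are taken off drug at 6 months, that 70% to 85% of subjects are on that path, that late rows therefore show mainly responders, and that a fading effect will appear as a growing one. The documents do not support this:

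- Protocol 6 asks for a discussion with the sponsor, not a stop, and gives no stopping share.
- The discussion applies only to subjects with neither HI-E nor TI. HI-E is broader than TI, so one minus the TI rate is an upper bound.
- In the 10% / 50% scenario, responders are only 44% (TI rate 30%) or 25% (TI rate 15%) of those left at Week 32.
- Where a deepening appears, it is one step followed by a flat or fading course.

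Three further objections stand in part. Prior burden is a maximum, so untreated subjects will usually fall somewhat below it, and 0% change for non-responders is a simplification. Time points are undefined, so a Week 32 row is itself an assumption, though follow-up to 1 year after the last randomization makes such rows possible. Off-drug data may be patchy: the schedule collects them where feasible, and Protocol 8.2 requires concomitant therapies, transfusions included, only to 30 days after dosing or the start of subsequent anticancer treatment. This limits what the remedy can recover but does not justify leaving out the data that are collected.

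**Conclusion.** The point holds as a bias of known direction and unknown size. Followed as written, the SAP drops subjects from later rows for reasons related to response, and those rows overstate the transfusion reduction in the ITT population if non-responders stop preferentially. At a true TI rate of 30%, the overstatement at Week 32 runs from 6 to 8 percentage points with 25% stopping at 6 months to about 35 points with 80%. These sizes rest on the assumed onset, duration and stopping shares. An apparent deepening beyond the early intervals needs a large share to stop: roughly half or more under the assumed fade to -60%, and somewhat less if the effect fades more slowly. It should not be presented as the expected result.

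The scope is one descriptive secondary summary. The primary 8-week TI rate and its decision rule are untouched. The change is still worth making, because this summary serves a stated objective and would be read more closely if the primary result were inconclusive.

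**What to change.** In SAP 6.2.2:

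- Define the time points as fixed successive 8-week intervals from Study Day 1 (Weeks 1-8, 9-16, 17-24 and so on).
- Summarise amount and relative change over all ITT subjects still under transfusion follow-up, on or off drug, using the post-treatment transfusion data, without the last dose + 30 days limit.
- Show the number on drug, off drug and missing at each interval.
- Add one sensitivity row that sets unobserved intervals after stopping to 0% change from prior burden.
- Keep the last dose + 30 days version as a supportive table labelled on-treatment.

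The cost is SAP wording and one extra table. No treatment rule changes, and no collection is needed beyond that in Protocol 9.2.1. The downside is small: off-drug data may be incomplete and can reflect subsequent therapy, which the counts and the on-treatment table make visible, and the late reductions will look less favourable.

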7. SAFETY

Safety analyses will be performed using the safety analysis set. The safety parameters to be evaluated are the incidence, intensity, and type of adverse events, clinically significant changes in the subject's physical examination findings, vital signs measurements, clinical laboratory results (hematology and chemistry), and deaths. Exposure to study treatment and reasons for discontinuation will be tabulated. Descriptive statistics will be reported for all safety data.

7.1. ADVERSE EVENTS

Treatment-emergent adverse events are adverse events that (1) occur after the first dose of study drug through the 30 days following the last dose of study drug or until subsequent anti-cancer therapy if earlier; (2) any adverse event considered study drug-related regardless of the start date of the event; or (3) any event present at baseline but worsens in severity or is subsequently considered drug-related by the investigator. Treatment-emergent adverse events will be summarized by System Organ Class and preferred term, by intensity (National Cancer Institute (NCI) common terminology criteria for adverse events (CTCAE), Version 4.03), and by study drug relationship.

For each treatment-emergent adverse event, the percentage of subjects who experience at least 1 occurrence of the given event will be summarized. Tables will be sorted by frequency in incidence (the highest to lowest incidence). The same summary will be provided for serious treatment-emergent AEs, and drug-related serious treatment-emergent AEs, as well as treatment-emergent AEs leading to treatment discontinuation, death, dose modifications or delays.

The verbatim terms used in the electronic case report form (eCRF) by investigators to identify AEs will be coded using the Medical Dictionary for Regulatory Activities (MedDRA).

7.3. CLINICAL LABORATORY TESTS

Laboratory data of hematology and clinical chemistry from baseline up to 30 days after last dose will be reported in SI units.

Summary statistics (N, mean, SD, median, and range) will be calculated for the raw data and for their changes from baseline by scheduled visits, as well as for last value and for the changes from baseline to the last value. Within a cycle, summary statistics from the worst values will be provided. Individual values outside the normal ranges will be identified (by "H" for high and "L" for low) in the data listings displaying the absolute values for each subject.

Displays of over-time summaries will be presented for the following key laboratory parameters: hemoglobin, platelet count, white blood cell count, manual absolute peripheral blast count, absolute neutrophil count (ANC), creatinine, total bilirubin (with fractionation if abnormal), ALT, AST, ALP, lactate acid dehydrogenase, and albumin.

Shift tables for each cycle will be produced for selected laboratory parameters, including hemoglobin, platelet count, white blood cell count, peripheral blast count, ANC, total bilirubin, ALT, AST, and ALP. These tables will summarize by cycle the number of subjects with each baseline CTCAE grade and changes to the maximum CTCAE grade in the cycle. For laboratory parameters without CTCAE grade, shifts from baseline to highest per cycle (Low, Normal, High) categories will be used.

Shift tables from baseline to worst value on treatment (from treatment start to 30 days after last dose or the end of treatment visit date, whichever is later) will also be provided. The worst toxicity grade during the treatment will be tabulated.

In addition, incidence of persistent (≥ 2 or 4 weeks) and severe (≥ 3 or 4 grade) cytopenia (thrombocytopenia/neutropenia) will be evaluated. Maximum post-baseline CTCAE V 4.03 grade for anemia, leukopenia, neutropenia, and thrombocytopenia will be tabulated.

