			Cycle 1 Day 1	Cycle 1 Day 8, 15, 22	Cycle 2 Day 1, 8, 15, 22	Cycle 3, 4, 5, 6 Day 1, 15	Cycle 7 until EOT Day 1	EOT Visit Within 30 days after last dose	
Study Procedures		Up to 28 days before first dose							Survival Follow-up Every 16 weeks (+/- 7 days)
Clinical Laboratory Assessments									
Hematology	Hematology laboratory assessments to determine subject eligibility must be performed within 14 days prior to first dose. For Cycle 1 Day 1, clinical laboratory assessments do not need to be repeated if the Screening tests were performed within 5 days of the first dose of study treatment.	X	X ^a	X	Only Day 1 ^a	Only Day 1 ^a	X	X	
Chemistry	Chemistry laboratory assessments to determine subject eligibility must be performed within 14 days prior to first dose. For Cycle 1 Day 1, clinical laboratory assessments do not need to be repeated if the Screening tests were performed within 5 days of the first dose of study treatment.	X	X ^a		Only Day 1 ^a	Only Day 1 ^a	X ^a	X	
Blood type assessment and indirect antiglobulin results	Prior to dosing on Day 1 of Cycle 1 only								
Serum EPO level		X							
Serum ferritin, transferrin saturation		X							
Serology	HIV antibody, hepatitis B surface antigen, and hepatitis C virus antibody	X							
Serum β -hCG or urine pregnancy test	For women of childbearing potential only; must be performed within 14 days prior to first dose	X	Only if clinically indicated						
Ongoing Subject Review									
Concomitant therapy	Continuous from the time of signing ICF until 30 days after the end of dosing or until the start of subsequent anticancer treatment, if earlier	X			Continuous			X	

TIME AND EVENTS SCHEDULE - DARATUMUMAB

PHASE	Notes	Screening Phase	Treatment Phase (4-week cycles +/-3 days)					Posttreatment Follow-up Phase	
		Up to 28 days before first dose	Cycle 1 Day 1	Cycle 1 Day 8, 15, 22	Cycle 2 Day 1, 8, 15, 22	Cycle 3, 4, 5, 6 Day 1, 15	Cycle 7 until EOT Day 1	EOT Visit Within 30 days after last dose	Survival Follow-up Every 16 weeks (+/- 7 days)
Adverse events	Continuous from the time of signing ICF until 30 days after the end of dosing or until the start of subsequent anticancer treatment, if earlier	X	Continuous					X	
Subsequent therapy	Subsequent therapy to be collected throughout survival follow-up period							X	X
Abbreviations: C1D1=Cycle 1, Day 1; CR=complete remission; CyTOF=cytometry by time of flight; EOT=end-of-treatment; EPO=erythropoietin; PD=disease progression; PR=partial remission									

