3.6. CHANGE IN STUDY CONDUCT

Enrollment to the talacotuzumab arm was closed based upon the occurrence of a Grade 4 infusion-related reaction in the first subject who received talacotuzumab. All analyses and summaries described in this document will include data only in subjects who received daratumumab. Data listings will be provided separately for the single subject who received talacotuzumab.

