4. GENERAL DESCRIPTIONS AND DEFINITIONS

4.1. BASELINE AND STUDY PHASES

Baseline Value: Unless specified otherwise, the baseline value is defined as the last non-missing value collected on or before the first dose.

Screening Phase: Up to 28 days prior to the first dose of study drug, during which subject eligibility will be reviewed and approved by the sponsor.

Treatment Phase: Between the date of first dose until study drug discontinuation. The Treatment Phase will be divided by cycles, based on the nominal treatment cycles as recorded on the CRF. Each cycle is planned to be 28 days.

Post-treatment Follow-up Phase: After the End of Treatment Phase until the end of study participation or end of study, which is defined as 1 year after randomization of the last subject or anytime the Sponsor terminates the study, whichever comes first.

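### The by-cycle laboratory tables compare unequal draws: Cycle 1 chemistry is set against its own baseline, and Cycle 1 cytopenia grades are inflated relative to later cycles

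*SAP*

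**What the plan says.** SAP 7.3 cuts laboratory data by cycle in two ways. For values, "Within a cycle, summary statistics from the worst values will be provided". For nine parameters ("hemoglobin, platelet count, white blood cell count, peripheral blast count, ANC, total bilirubin, ALT, AST, and ALP") it plans shift tables that give, cycle by cycle, the baseline grade and "changes to the maximum CTCAE grade in the cycle". SAP 4.1 fixes both ends of the shift: "the baseline value is defined as the last non-missing value collected on or before the first dose", and "The Treatment Phase will be divided by cycles, based on the nominal treatment cycles as recorded on the CRF". SAP 3.6 adds: "All analyses and summaries described in this document will include data only in subjects who received daratumumab". The daratumumab Time and Events Schedule therefore governs.

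That schedule places hematology on Days 1, 8, 15 and 22 of Cycle 1 and on Day 1 only of later cycles. It places chemistry on Day 1 only in every cycle, with the cell for Cycle 1 Days 8, 15 and 22 blank. A footnote makes the marked draws pre-infusion, and Protocol 9.1.3 makes visit procedures pre-dose by default. The Cycle 1 Day 1 draw may be omitted if screening tests fell within 5 days of the first dose. Protocol 9.2.2 separately asks for weekly hemoglobin over the first 8 weeks.

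SAP 7.3 also plans summaries by scheduled visit, over-time displays of key parameters, and a shift table to the worst value on treatment.

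**The concern.** A by-cycle shift table is read as the course of cytopenia and liver tests with time on drug. That reading needs each column to rest on a similar number of draws at a similar point in dosing. Here the columns differ in both respects, and the SAP makes no allowance for it.

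Two misreadings follow. The liver columns would show a quiet Cycle 1, although four infusions are given in that cycle. The cytopenia columns would tend to show an early peak that then subsides, even if nothing changed. Only one arm is analysed, so no comparator on the same schedule would expose the pattern. The by-visit summaries that 7.3 describes give means, medians and ranges, so the by-cycle shift tables are the display it describes as grades against time.

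**Working it through.** The documents give no figure for these tables, so there is none to reproduce.

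**1. Scheduled draws per nominal cycle** (daratumumab schedule; last row from Protocol 9.2.2)

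| Parameter | Cycle 1, pre-dose Day 1 | Cycle 1, after first infusion | Cycle 2 | Each later cycle |
|---|---|---|---|---|
| Platelets, ANC, WBC, blasts | 1 | 3 | 1 | 1 |
| ALT, AST, ALP, bilirubin | 1 | 0 | 1 | 1 |
| Hemoglobin, per schedule | 1 | 3 | 1 | 1 |
| Hemoglobin, per 9.2.2 | 1 | about 3 | about 4 | 1 |

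**2. Chemistry.** No assumption is needed. The pre-dose Day 1 value is the last value on or before first dose, so it is the baseline. It is also the only scheduled value in nominal Cycle 1. The scheduled shift is baseline minus itself, which is zero. If the Day 1 draw is omitted, the screening value is the baseline and Cycle 1 has no scheduled value at all. The first value that can reflect Cycle 1 dosing is Cycle 2 Day 1, drawn before the Cycle 2 infusion but filed under Cycle 2. The same one-cycle displacement continues in later cycles.

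**3. Platelets, ANC, WBC and blasts.** Let p be the chance that any one draw reaches a given grade, constant over time, and k the number of draws in the cycle.

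- Independent draws: P(worst of k reaches the grade) = 1 − (1 − p)^k. For p = 5%, 1 − 0.95³ = 14.3% and 1 − 0.95⁴ = 18.5%.
- Correlated draws: the same quantity averaged over a shared normal subject effect, with within-subject correlation ρ.

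Neither p nor ρ is in the documents. Both are assumptions, shown as a range. Subject counts use the planned N = 30.

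| p | ρ | k = 1 | k = 3 | k = 4 | Subjects of 30 (k = 1 / 3 / 4) | Ratio to k = 1 (k = 3 / 4) |
|---|---|---|---|---|---|---|
| 5% | 0 | 5.0% | 14.3% | 18.5% | 1.5 / 4.3 / 5.6 | 2.9 / 3.7 |
| 10% | 0 | 10.0% | 27.1% | 34.4% | 3.0 / 8.1 / 10.3 | 2.7 / 3.4 |
| 10% | 0.8 | 10.0% | 17.2% | 19.3% | 3.0 / 5.2 / 5.8 | 1.7 / 1.9 |
| 10% | 0.9 | 10.0% | 15.0% | 16.3% | 3.0 / 4.5 / 4.9 | 1.5 / 1.6 |
| 20% | 0.8 | 20.0% | 31.3% | 34.3% | 6.0 / 9.4 / 10.3 | 1.6 / 1.7 |
| 30% | 0.9 | 30.0% | 39.6% | 41.9% | 9.0 / 11.9 / 12.6 | 1.3 / 1.4 |

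The post-dose contrast is k = 3 against k = 1. The k = 4 column applies if the pre-dose Day 1 draw is left in the maximum. With one draw in every cycle the expected result is flat at p.

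**4. A second illustration.** This uses log-normal counts with no trend, assumed between-subject CV 50%, assumed within-subject CV 20–40%, and a Day 1 value that meets the entry limit in Protocol 4.1. Because Day 1 cannot then fall below the limit, this too is a 3-against-1 contrast. Cycle 1 against Cycle 2:

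- ANC below 1.0 × 10⁹/L, median 2.0: 8–19% against 4–8%
- ANC below 1.0 × 10⁹/L, median 1.5: 16–32% against 8–16%
- Platelets below 50 × 10⁹/L, median 80: 14–29% against 7–14%

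The apparent rate roughly halves after Cycle 1 with nothing changing.

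**5. Hemoglobin.** The schedule restricts Cycle 2 hematology to Day 1; Protocol 9.2.2 implies about four hemoglobin values in Cycle 2. Under 9.2.2 the count drops between Cycles 2 and 3, not between Cycles 1 and 2.

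**The case against.** The strongest reply is that nothing is lost. By-visit summaries show Cycle 1 Days 8, 15 and 22 separately and show Cycle 2 Day 1 chemistry after the first month of dosing. The over-time displays, the worst-on-treatment shift table, the maximum post-baseline grades and the adverse event tables cover the rest. All safety analyses are descriptive, and no decision criterion uses the by-cycle tables. Filing a Day 1 draw under the cycle it opens is a nominal-cycle convention. Replacing worst-in-cycle would also remove the Cycle 1 nadirs. Most of this stands: it confines the problem to the by-cycle displays and argues for keeping the worst-in-cycle table. It does not make those displays interpretable over time.

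The second reply also has force. SAP 7.3 does not restrict the maximum to scheduled draws. Protocol 6.3.5 requires a toxicity evaluation before each daratumumab dose. Protocol 9.5 requires the onset and most abnormal values of any laboratory abnormality reported as an adverse event. Clinically prompted values can therefore enter Cycle 1 chemistry and later-cycle hematology, and an end-of-treatment draw may fall in the last cycle.

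A reader might go further and infer that the whole by-cycle trend is dictated by the schedule, or that a first-month liver signal would go unseen. The documents do not support either reading, for the reasons just given. Nor do they support a four-against-one post-dose contrast, since the fourth Cycle 1 draw is the baseline and may be omitted. A fall in severe low hemoglobin from Cycle 1 to Cycle 2 cannot be claimed as an artefact either, because 9.2.2 gives both cycles about the same number of values.

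**Conclusion.** The point holds for the by-cycle displays in SAP 7.3. For scheduled Cycle 1 chemistry it is exact and free of assumptions: the shift is zero or missing by definition. For platelets, ANC, WBC and blasts the direction is certain when per-draw risk is constant and only scheduled draws are counted. The size is not known. It is about 1.3 to 2.9 times for three draws against one, and up to 3.7 times with the pre-dose draw included, over p of 5–30% and ρ of 0–0.9. Any real trend would be mixed with this artefact. For hemoglobin the two protocol passages disagree on Cycle 2 and must be reconciled before the draw counts can be stated. This should be corrected in the SAP, but it has no bearing on the efficacy conclusion or on the overall safety summary.

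**What to change.** In SAP 7.3:

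- (a) Exclude the pre-dose Cycle 1 Day 1 value from every post-baseline or Cycle 1 maximum.
- (b) Assign each pre-dose Day 1 laboratory value to the cycle just completed, so that Cycle 2 Day 1 chemistry is reported as the Cycle 1 result.
- (c) Add a by-cycle shift table using one matched scheduled value per cycle: the next cycle's pre-dose Day 1, or end of treatment for the last cycle. Use this table for comparisons across cycles.
- (d) Keep the worst-in-cycle table for nadirs, print the number of draws per cycle, and state that it is not to be read as a time trend.

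Items (c) and (d) are needed even after (b). Under (b) Cycle 1 hematology holds Days 8, 15 and 22 plus Cycle 2 Day 1, so four post-dose values stand against one in later cycles. Reconcile Protocol 9.2.2 with the schedule on Cycle 2 hemoglobin.

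The cost is one extra table and a derivation that departs from nominal CRF cycle labels. Values from end of treatment (within 30 days of the last dose) and from delayed cycles will match only approximately in timing. No new data are needed.
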